### **13.33 Analysis of Efficacy**

If there are 1 or fewer deaths from tumor progression, within 10 patients, with 3 years median follow up, then a presumption can be made that the reduction in radiation dose has not led to a decline in efficacy. The information would then be supplied to the national group (Children's Oncology Group) as a potential next national Phase III, randomized study.

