## **2.0 OVERVIEW AND STUDY DESIGN**

This study is to look at the efficacy of reducing the dose of craniospinal radiation to limit adverse effects, while adding concurrent carboplatin administration during radiation with weekly vincristine for metastatic medulloblastomas and high-risk supratentorial PNETs and metastatic PNETs. Pilot data from Children's Oncology Group (COG) study 99701 show excellent results with daily carboplatin infusion during radiation for high risk central nervous system tumors (Jakacki et al, 2006). This study had an 89% 3 year event free survival for classical histology metastatic medulloblastoma. Anaplastic medulloblastomas did poorly and will be excluded from the current study.

Although the COG 99701 study had excellent event free survival, 36 Gy radiation dose to the craniospinal axis was used. This dosage is known to be associated with extremely poor quality of life as an adult (Ribi et al, 2005, Packer et al, 1994). The improvement of survival of COG 99701 over all prior studies appears to be due to the addition of carboplatin during radiation. The current study proposes to see if the addition of carboplatin during radiation allows for lowering the craniospinal radiation dose to 23.4 Gy, a dose which is known to be associated with a satisfactory quality of life for adult survivors (Ribi et al, 2005, Packer et al, 1994).

In order to assess efficacy we would accept equivalency in terms of 90% event free survival from progression at 3 years. We will re-assess the therapy after every 10 patients completes the study. One

failure within every ten patients would close the study. Following concurrent carboplatin, vincristine, and craniospinal radiation at 24 Gy, patients will receive the current standard adjuvant chemotherapy.

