## 13.0 **STATISTICAL CONSIDERATIONS**

This is a pilot study of concurrent carboplatin (CARBO), vincristine (VCR), and radiation therapy (XRT) followed by standard of care maintenance VCR and cyclophosphamide (CPM) ± cisplatin (CDDP) in children aged 3 to 25 years with metastatic medulloblastoma, high risk PNET and metastatic PNET. Eligible patients comprise those with supratentorial PNET and infratentorial PNET/MB with initial stage M1-M4 or >1.5cc residual tumor remaining after surgery and classical histology.

The primary objective of the protocol and the statistical analysis is to obtain preliminary estimates of event free survival (EFS) and to demonstrate less decrement in intellectual function in preparation for a future Phase III randomized trial including these treatments.

Statistical considerations for the primary objective are addressed below.

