## **13.2 Study Duration**

We originally anticipated that it would require approximately 24 months to complete accrual to this study. However, at this time we are more accurately anticipating to complete enrollment by 2016.

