## **13.3 Study Endpoints**

### **13.31 Efficacy Endpoints**

**Event-free survival:** Minimum time to disease progression or recurrence, time to death for any reason, or time to occurrence of a second malignant neoplasm (SMN).

**Overall Survival:** Time to death from any cause.

**Intellectual Competence:** Performance is as good as or better than patients treated on CCG 9961 when adjusted for baseline performance

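### The efficacy rule in 13.33 counts only tumour-progression deaths, although the protocol's standard is 90% event-free survival at 3 years, so patients alive after relapse are not counted as failures

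*Protocol*

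**What the plan says.** **Standard.** Protocol 2.0 states that "we would accept equivalency in terms of 90% event free survival from progression at 3 years". The benchmark beside it is a cooperative-group study that used 36 Gy to the craniospinal axis: "This study had an 89% 3 year event free survival for classical histology metastatic medulloblastoma".

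**Objective and endpoint.** Section 13.0 makes preliminary estimation of EFS a primary objective, together with intellectual function. Section 13.31 defines an EFS event as the first of progression or recurrence, death from any cause, or a second malignancy. It lists overall survival separately, with death from any cause as the event.

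**Decision.** Section 13.33 sets the condition "If there are 1 or fewer deaths from tumor progression, within 10 patients, with 3 years median follow up". When it is met, "a presumption can be made that the reduction in radiation dose has not led to a decline in efficacy", and the result goes to the national group as a potential Phase III study.

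**Related rule.** Section 13.41 expects survival of about 90% and accepts one failure in ten as equivalent, without saying what a failure is. It then counts tumour deaths for closure. It also suspends the study for any toxic death.

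**The concern.** The quantity that decides (tumour deaths) is neither of the time-to-event endpoints in 13.31. It is narrower than EFS, and narrower than overall survival. One failure in ten corresponds to the 90% EFS standard only if a failure is an EFS event.

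The trial lowers the craniospinal dose in high-risk patients, so loss of disease control is the risk that an efficacy rule has to detect. A patient whose tumour has recurred but who is alive at the reading does not count against the regimen under 13.33. The protocol can then conclude that efficacy has not declined while its own EFS estimate, a primary objective, lies well below 90%.

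**Working it through.** **Inputs.** n = 10 (13.1); pass if the count is 1 or fewer (13.33); standard 90% EFS at 3 years (2.0); event definition (13.31). The share s of 3-year EFS events that are tumour deaths within the window is not in the protocol, so it is an assumption shown as a range.

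**The plan's own figure.** 1 − 1/10 = 0.90 and 1 − 2/10 = 0.80. One in ten matches 90% when every EFS event is counted. The protocol states no error rate or power for this rule, so there is none to reproduce.

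**Direction.** A patient who dies of tumour progression has progressed, and so has already had an EFS event. Within one window, tumour deaths ≤ EFS events. No outcome can fail 13.33 and pass a count of EFS events; the reverse can happen. This needs no value for s. It also holds if 2.0 is read narrowly as freedom from progression, since a tumour death still requires progression.

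**Example.** Ten patients, 4 relapses, 1 tumour death. The 13.33 count is 1, a pass. Observed EFS is 1 − 4/10 = 60%, exact (Clopper-Pearson) 95% CI 26.2% to 87.8%.

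**Pass probability.** P(X ≤ 1) = (1 − p)^10 + 10p(1 − p)^9, with p = s(1 − EFS). Setting s = 1 gives the count of all EFS events. At EFS 70% and s = 0.75, p = 0.225 and P = 0.078 + 0.227 = 0.305.

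| True 3-year EFS | s = 1 (all EFS events) | s = 0.9 | s = 0.75 | s = 0.5 |
|---|---|---|---|---|
| 90% | 0.736 | 0.775 | 0.830 | 0.914 |
| 80% | 0.376 | 0.439 | 0.544 | 0.736 |
| 70% | 0.149 | 0.202 | 0.305 | 0.544 |

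The chance of passing 13.33 while failing the EFS count is the difference from the s = 1 column. At EFS 80% it is 0.544 − 0.376 = 0.168 for s = 0.75 and 0.736 − 0.376 = 0.360 for s = 0.5. At EFS 70% it is 0.156 and 0.395.

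**Window.** Section 13.33 reads at a median follow-up of 3 years, not at 36 months for each patient. About half the patients then have less than 36 months, which lowers the count further. The others have more, so their later tumour deaths can enter. Let q be the rate of tumour death by the reading among patients event-free at 36 months. The expected tumour-death count equals the expected 36-month EFS count when s(1 − EFS) + q·EFS = 1 − EFS, so q = (1 − EFS)(1 − s)/EFS. At EFS 80% this is 0.05/0.80 = 6% for s = 0.75 and 0.02/0.80 = 2.5% for s = 0.9.

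**The case against.** - **The document carries more than one 90% standard.** This stands. Section 13.41 ties one in ten to survival and leaves failure undefined. A reader might infer that 13.33 is the only efficacy rule and a lone slip; 13.41 shows otherwise. The defect is an inconsistent definition of failure across 2.0, 13.33 and 13.41.
- **Section 2.0 qualifies its standard as event-free from progression.** Read narrowly, second malignancies and non-tumour deaths lie outside it, and leaving them out does not contradict 2.0. That also stands, but relapsed living patients remain a gap under either reading, and 13.31 uses the full definition.
- **Toxic deaths are not ignored.** Correct: 13.41 suspends the study for them. They still do not enter the 13.33 count.
- **The size depends on an unstated share.** Correct. A reader might infer that the rule is far too lenient in practice. The documents do not support a particular figure: at s = 1 the gap is zero.
- **Late deaths can work the other way.** Correct, and when s is near 1 a small late-death rate is enough. The claim that the rule is never harder is therefore limited to a common window.
- **It is a 10-patient pilot, and EFS will be reported anyway.** True, and a low EFS would be visible. But 13.33 states a conclusion about efficacy that such an estimate could contradict, and correcting the endpoint takes no more patients.

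**Conclusion.** The point holds. Section 13.33 decides on an endpoint that matches neither the standard in 2.0 nor either survival endpoint in 13.31. Over a common window its count cannot exceed the EFS count, and it is smaller whenever a relapsed patient is alive. Under the full 13.31 definition it is also smaller when a patient has had a second malignancy or has died of another cause.

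The direction follows from the definitions alone. The size rests on independent patients, a binomial count and an assumed s. At true EFS 70% the pass probability is 20% (s = 0.9), 31% (0.75) or 54% (0.5), against 15% when all EFS events count. Deaths after 3 years in early patients can partly offset the gap, because the reading is at median follow-up.

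Correcting the endpoint does not cure the imprecision of 10 patients. A true EFS of 80% would still pass 38% of the time, so a pass cannot show that efficacy is unchanged.

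**What to change.** 1. In 13.33, count EFS events as defined in 13.31, from enrolment through each patient's 36-month visit on the 6.5 schedule. That schedule runs from the end of radiotherapy, so 36 months from enrolment would fall before the 36-month scan.
2. Read the rule when every patient has reached that visit, had an event or left follow-up. Report the count with event-free withdrawals taken once as failures and once as non-failures: one event plus one such withdrawal gives 2 or 1, on either side of the limit. Give the Kaplan-Meier 3-year EFS with its 95% CI beside it.
3. Keep the limit of 1 or fewer of 10, but state that meeting it supports randomised testing and does not show that efficacy has not declined. One event in 10 gives EFS 90% with an exact 95% CI of 55.5% to 99.7%.
4. Keep collecting event status for event-free patients who leave under 9.2(c) to a follow-up study. Patients who enter second-line treatment after progression already have an event.
5. Use one definition of failure in 2.0, 13.33 and 13.41.

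The number of failures that closes the study also differs between 2.0 and 13.41. That is a separate matter: the passages must be reconciled, and no closure rule is proposed here.

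**Cost.** No extra patients. A regimen with true 90% EFS would miss the count 1 − 0.736 = 26% of the time, against 23%, 17% or 9% under the present count at s = 0.9, 0.75 or 0.5. The reading comes later. With even accrual over the 24 months first planned in 13.2 (an assumption, since that section now expects enrolment to end by 2016), a 36-month median falls at month 48, while the last patient reaches 36 months at month 60. That is 12 months later, plus the weeks from enrolment to the end of radiotherapy. The stated conclusion is also less favourable.

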## **13.4 Interim Monitoring**

### **13.41 Interim Monitoring of Treatment Efficacy**

Because of the short duration of this study, therapeutic efficacy as measured by either EFS or survival, will not be subject to interim monitoring. The first formal analysis of this study will occur when median follow-up is approximately 18 months. The formal early monitoring of dose limiting toxicities and any toxic deaths will provide early warning of significant safety problems.

Because we expect a survival of approximately 90%, if there is one failure in ten patients, we will accept that as equivalent. If there are 2 deaths from tumor progression within the first 10 patients, the study will be closed. All patients will subsequently be monitored. If there are no further deaths and the number of patients is still less than 10, the study will be re-opened to accumulate a total of 10 patients. The expectation is that there will be no toxic deaths. Any toxic deaths will result in the suspension of the study, investigation into the cause of death, and discussion with the IRB.

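### The success rule counts tumor deaths at a median of 3 years of follow-up, so it does not measure the 3-year event-free rate that it is meant to check

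*Protocol*

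**What the plan says.** Protocol section 2.0 states the efficacy standard at a fixed time: "In order to assess efficacy we would accept equivalency in terms of 90% event free survival from progression at 3 years". The historical figure beside it has the same horizon: "This study had an 89% 3 year event free survival for classical histology metastatic medulloblastoma".

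Section 13.33 gives the rule for declaring success: "If there are 1 or fewer deaths from tumor progression, within 10 patients, with 3 years median follow up". If that condition is met, the protocol presumes that efficacy has not declined with the lower dose, and the result would go to the national group as a possible randomized Phase III trial. Section 13.41 gives the reason for the cut-off: "Because we expect a survival of approximately 90%, if there is one failure in ten patients, we will accept that as equivalent".

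On timing, section 13.2 gives an original accrual period of about 24 months and then says: "However, at this time we are more accurately anticipating to complete enrollment by 2016". It does not say how long accrual will have taken. Section 6.5 schedules follow-up visits to 60 months after radiotherapy.

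No section sets a minimum follow-up per patient for the success rule, or says how a patient followed for less than 3 years is counted.

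**The concern.** A 3-year event-free rate is a probability at one time point. The rule in section 13.33 is a count out of ten, taken when the median follow-up is 3 years. These differ in two ways that pull in opposite directions. A patient with, say, 2 years of follow-up and no tumor death counts as a full success, although a year of risk remains. A patient who dies of tumor in year 4 counts as a failure, although that patient was alive at the 3-year horizon.

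Which effect dominates depends on how patients enter and when failures happen, and the rule controls neither. The same true 3-year rate can therefore give quite different chances of passing. At stake is the statement that the lower craniospinal dose has not reduced efficacy, and the recommendation that would follow from it.

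**Working it through.** **The plan's own figures.** One failure in ten is 1 − 1/10 = 0.90, which reproduces the 90% in section 13.41. Ten patients at 5 per year (section 13.1) is 10/5 = 2 years, which reproduces the 24 months in section 13.2. No error rate or power is stated for the rule, so there is none to reproduce.

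**How many can be short of 3 years.** With ten patients the median is the mean of the 5th and 6th ordered follow-up times. A median of 3.0 years is compatible with five patients below 3 years. Under even accrual over 24 months without early loss, follow-up at that moment runs 2.1, 2.3, …, 3.9 years, and five of ten are below 3.

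**Assumptions.** The documents give no hazard shape and no alternative event rate, so these are assumed and varied:
- True 3-year rate S of 70%, 80% or 90%.
- Constant hazard up to 3 years, so the failure probability at follow-up t ≤ 3 is q = 1 − S^(t/3).
- After 3 years, either no further failures (plateau) or the same hazard continuing.
- Even accrual over 2 years (stated in the protocol), or over 4 or 6 years (assumed), always with median 3.0.
- One pattern with a long upper tail: four patients at 2.5 years, two at 3 and four at 6 (assumed; median still 3.0).
- One failure event for both benchmark and rule. The protocol's benchmark is event-free survival and its rule counts tumor deaths; that mismatch is a separate matter.

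**Formula.** For independent patients, P(pass) = P(at most 1 failure) = Π(1 − qᵢ) × [1 + Σ qᵢ/(1 − qᵢ)].

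**Numbers at S = 0.70.**
- All ten scored at 3 years: 0.7^10 × (1 + 10 × 0.3/0.7) = 0.02825 × 5.286 = 0.149.
- 24-month accrual, plateau: years at risk, capped at 3, sum to 12.5 + 15 = 27.5, so Π = 0.7^(27.5/3) = 0.03802. The odds sum to 3.877. P = 0.03802 × 4.877 = 0.185.
- Long-tail pattern, hazard continuing: years sum to 10 + 6 + 24 = 40, so Π = 0.7^(40/3) = 0.00860. With q = 0.257, 0.300 and 0.510 the odds sum to 1.385 + 0.857 + 4.163 = 6.405. P = 0.00860 × 7.405 = 0.064.

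The other cells use the same formula:

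| Follow-up at the reading (median 3.0) | After year 3 | S = 70% | S = 80% | S = 90% |
|---|---|---|---|---|
| All ten scored at 3 years | – | 0.149 | 0.376 | 0.736 |
| 2-year accrual (stated) | plateau | 0.185 | 0.423 | 0.767 |
| 4-year accrual (assumed) | plateau | 0.230 | 0.476 | 0.798 |
| 6-year accrual (assumed) | plateau | 0.286 | 0.535 | 0.830 |
| 2- to 6-year accrual | same hazard | 0.150–0.158 | 0.377–0.387 | 0.737–0.743 |
| Four at 2.5, two at 3, four at 6 years (assumed) | same hazard | 0.064 | 0.233 | 0.620 |

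The direction can reverse on event timing alone. For the pattern in the last row at S = 70%, a plateau gives Π = 0.7^(28/3) = 0.0358, odds summing to 1.385 + 2.571 = 3.956, and P = 0.0358 × 4.956 = 0.178. That is above 0.149, where the continuing hazard gave 0.064.

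**The case against.** The strongest reply is that a reader might infer that a median reading always favours the reduced dose. The documents do not support that. The rule counts tumor deaths whenever they occur before the reading, including those after year 3. With constant hazard and evenly spread follow-up these almost exactly offset the missing early time, and with a long upper tail of follow-up the rule becomes stricter. This objection stands in full, so no direction is claimed here.

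Second, the size is uncertain. The only accrual length in the protocol is 24 months, and under it even a complete plateau moves 0.149 only to 0.185 at a true 70%. Section 13.2 shows that the estimate was revised but gives no length, and nothing says that entry was weighted towards the end. A hard plateau is also less plausible for tumor deaths, which follow progression, than for event-free survival. With half the hazard after year 3, the 2-, 4- and 6-year figures at 70% are 0.167, 0.188 and 0.213. This also stands: the larger figures illustrate sensitivity and are not estimates for this trial.

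Third, one might read the analysis planned in section 13.41 ("The first formal analysis of this study will occur when median follow-up is approximately 18 months") as an occasion for declaring success. Section 13.33 ties the success statement to a 3-year median, so that reading is not supported.

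Fourth, this is a pilot of ten patients whose result is only a presumption. Even with complete 3-year follow-up the rule passes with probability 0.376 at a true 80%, so sample size limits it more than spread of follow-up does under the stated accrual. That bears on how much weight the point deserves. It does not make the count a measure of the 3-year rate.

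**Conclusion.** The point holds as a mismatch between benchmark and rule. The protocol fixes its benchmark at 3 years, but its success rule is an uncensored count at a median of 3 years, with no minimum follow-up. Up to five of ten patients can be scored as successes before the horizon, and deaths beyond it count as failures.

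At an assumed true 3-year rate of 70%, the chance of passing is 0.149 on a true 3-year reading. It ranges from 0.064 to 0.286 over the accrual and hazard patterns examined, and from 0.150 to 0.185 under the stated 24-month accrual. These figures rest on assumed true rates, hazard shapes and longer accrual patterns, on independent patients with no early loss, and on treating the benchmark event and the counted event as the same. The need to fix the reading time does not depend on those assumptions.

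**What to change.** Amend section 13.33 in one of two ways:

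1. Score each patient at a fixed 3 years, and read the rule once every event-free patient has at least 3 years of follow-up. State that a death after 3 years does not count towards this rule and how a patient lost before 3 years is handled.
2. Base the statement on the Kaplan-Meier estimate of 3-year event-free survival with its confidence interval, so that shorter follow-up is treated as censored.

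The 36- to 60-month visits in section 6.5 already supply the follow-up, so no new data collection is needed. The cost is protocol wording and, under the first option, an efficacy statement that waits until the last event-free patient reaches 3 years.

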## **13.4 Interim Monitoring**

### **13.41 Interim Monitoring of Treatment Efficacy**

Because of the short duration of this study, therapeutic efficacy as measured by either EFS or survival, will not be subject to interim monitoring. The first formal analysis of this study will occur when median follow-up is approximately 18 months. The formal early monitoring of dose limiting toxicities and any toxic deaths will provide early warning of significant safety problems.

Because we expect a survival of approximately 90%, if there is one failure in ten patients, we will accept that as equivalent. If there are 2 deaths from tumor progression within the first 10 patients, the study will be closed. All patients will subsequently be monitored. If there are no further deaths and the number of patients is still less than 10, the study will be re-opened to accumulate a total of 10 patients. The expectation is that there will be no toxic deaths. Any toxic deaths will result in the suspension of the study, investigation into the cause of death, and discussion with the IRB.

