### 13.1 **Patient Accrual**

The Neuro-Oncology Program at Children's Hospital Colorado has seen an average of 5 patients per year with metastatic medulloblastoma, high risk PNET and metastatic PNET. We expect to enroll 10

patients. The current standard of care CCG 9961 was based on a pilot study of 10 patients (Goldwein et al, 1996).

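### Section 13.41 waives interim efficacy monitoring because the study is short, although 13.2 has lengthened accrual; the remaining stopping statements in 2.0 and 13.41 conflict, and non-fatal relapse has no stated consequence in 13.41

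*Protocol*

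**What the plan says.** - **Waiver (Protocol 13.41).** "Because of the short duration of this study, therapeutic efficacy as measured by either EFS or survival, will not be subject to interim monitoring". The same paragraph places the first formal analysis at a median follow-up of about 18 months.
- **Closure rule (13.41, second paragraph).** One failure in ten is accepted as equivalent. Then: "If there are 2 deaths from tumor progression within the first 10 patients, the study will be closed". The text foresees re-opening if fewer than ten patients have been enrolled, so this rule is meant to act during accrual.
- **Duration (13.2).** An accrual period of some 24 months is given as the initial estimate and then replaced: "at this time we are more accurately anticipating to complete enrollment by 2016".
- **Size and rate (13.1).** The programme "has seen an average of 5 patients per year with metastatic medulloblastoma, high risk PNET and metastatic PNET", and "We expect to enroll 10" patients is the plan. Section 4.2 also gives about ten.
- **Re-assessment (2.0).** "We will re-assess the therapy after every 10 patients completes the study". The next sentence closes the study on one failure in every ten patients. The word 'failure' is not defined.
- **Endpoint (13.31).** EFS counts progression or recurrence, death from any cause, and second malignancy. Section 13.0 makes estimation of EFS part of the primary objective, and 2.0 sets the target at 90% at three years.
- **Data (6.5).** MRI is scheduled repeatedly from 4 to 60 months after radiotherapy, with a further evaluation at relapse.

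**The concern.** The waiver rests on a single reason, short duration, and 13.2 withdraws the estimate behind it. The longer accrual runs, the more outcome information from early patients exists before later ones enter. That is the situation in which a plan should say what is done with such information.

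The rest of the text does not settle it. A re-assessment after every ten completers comes after the last planned patient has entered. Section 13.41 says survival is not monitored and then sets a rule that depends on counting tumour deaths. Section 2.0 may close the study on one event where 13.41 tolerates one. The explicit trigger in 13.41 is death from tumour, which follows progression, although the study's own efficacy endpoint counts the progression.

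The trial tests a reduced craniospinal dose in high-risk disease, so lost tumour control is the main efficacy risk and relapse is its earlier signal. As written, two investigators could read the same first or second relapse as requiring closure, or nothing.

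**Working it through.** **1. The plan's own duration.** 10 patients / 5 per year = 2 years = 24 months. This reproduces the original estimate in 13.2, which is the duration on which 'short' could rest. The document gives no start date, so the length of accrual to 2016 cannot be computed and is treated below as an assumption.

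**2. Do the two closure statements agree?** Take ten patients, each failing independently with probability p. In the second rule, count every failure as a tumour death.

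- Section 2.0, at least one failure: 1 − (1 − p)^10. At p = 0.10, 1 − 0.349 = 0.651. At p = 0.30, 0.972.
- Section 13.41, at least two: 1 − (1 − p)^10 − 10p(1 − p)^9. At p = 0.10, 1 − 0.349 − 0.387 = 0.264. At p = 0.30, 0.851.

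At the protocol's target of 90%, one sentence would close the study about 65% of the time and the other about 26%. They are not two wordings of one rule.

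**3. How much earlier would EFS events show a problem?** Assumptions: ten evenly spaced entries over A years; exponential time to progression with rate λ = −ln(S)/3, where S is the 3-year EFS; exponential time from progression to death with a mean of one year (rate μ = 1). A is 1.8 years (nine intervals at 5 per year) or 4 years. Patient i has been followed for tᵢ years when the tenth patient enters.

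- EFS event by then: 1 − exp(−λtᵢ).
- Tumour death by then: 1 − [μ exp(−λtᵢ) − λ exp(−μtᵢ)] / (μ − λ).
- Two or more: 1 − P(none) − P(exactly one), over the ten patients.

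Worked case, S = 0.70 and A = 4: λ = 0.357/3 = 0.1189. The follow-up times sum to 20 patient-years, so P(none) = exp(−2.378) = 0.093. P(exactly one) = 0.263. P(two or more) = 1 − 0.093 − 0.263 = 0.64.

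Probability of a second event before the tenth entry:

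| True 3-year EFS | Accrual | Two EFS events | Two tumour deaths |
|---|---|---|---|
| 50% | 1.8 y | 0.57 | 0.18 |
| 50% | 4 y | 0.93 | 0.73 |
| 70% | 1.8 y | 0.26 | 0.06 |
| 70% | 4 y | 0.64 | 0.39 |
| 90% | 1.8 y | 0.04 | 0.01 |
| 90% | 4 y | 0.14 | 0.06 |

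Sensitivity to the lag, at EFS 70% and 4 years: a mean of 0.5, 1 or 2 years gives 0.51, 0.39 or 0.24 for two deaths, against 0.64 for two EFS events. The direction does not change.

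**4. Where does the 18-month analysis fall?** With A = 4 the entries are 0.44 years apart. If median follow-up counts patients enrolled to date, it reaches 1.5 years between about year 2.6 and year 2.8, with six or seven enrolled, so the analysis falls within accrual. If it counts all ten, the analysis cannot precede the tenth entry at year 4, when median follow-up is already 4 − 2 = 2.0 years. The text does not say which is meant.

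**The case against.** A reader might infer that relapses during the longer accrual trigger no review at all. The documents do not support that.

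- Section 2.0 closes the study on one failure in ten. Because that section measures efficacy as event-free survival from progression, 'failure' may well include relapse. On that reading a single relapse closes the study.
- The two-death rule in 13.41 operates while enrolment is open.
- The 18-month analysis may fall within accrual.
- Section 9.1 lists progression as a reason to leave protocol therapy, so at a single centre a relapse would not go unnoticed.

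It can also be said that the waiver means only that no formal interim test is planned, which is ordinary in a ten-patient pilot, and that an EFS-based pause is a matter of preference. The gain is modest in patient numbers: under EFS 70% and 4-year accrual, mean enrolment when the rule acts is 7.9 with two EFS events against 9.0 with two deaths, and 9.3 against 9.9 with 1.8-year accrual.

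Much of this stands. It rules out the broad reading, and it leaves the choice of threshold to the sponsor. It does not restore the stated reason for the waiver. Nor does it reconcile one failure closing the study in 2.0 with one failure accepted in 13.41, or say what a relapse requires under 13.41.

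**Conclusion.** The point holds in this form. The waiver depends on a duration that 13.2 has withdrawn, and it contradicts the closure rule in its own section. The re-assessment in 2.0 is not an interim look. Sections 2.0 and 13.41 set incompatible closure statements around an undefined 'failure' (0.651 against 0.264 at a 10% failure rate). Section 13.41 attaches no consequence to non-fatal relapse.

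The contradictions are in the text and need no assumptions. The size of the delay does: 0.64 against 0.39 rests on assumed EFS of 70%, 4-year accrual, even entry, constant hazards and a one-year mean lag. It compares EFS events with the two-death rule alone, leaving aside the one-failure sentence and the 18-month analysis. It should be read as an illustration of direction and rough size. This should be corrected, but it does not show that the study runs without any safeguard.

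**What to change.** 1. Delete the short-duration waiver from 13.41.
2. Replace both sentences in 2.0 (re-assessment after every ten patients, and closure on one failure) and the closure text in 13.41 with one monitoring rule, stated once and cross-referenced. Define 'failure' in it. Changing only one of the 2.0 sentences would leave competing rules in force.
3. State that EFS events, as defined in 13.31, are reviewed as they occur while enrolment is open. The sponsor should set the number that pauses enrolment and report the chance of pausing a regimen that meets its target. For example, a pause at a second event would occur with probability of about 0.14 over an assumed 4 years at true EFS of 90%.
4. State whether the 18-month median follow-up counts patients enrolled to date or all ten.

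The cost is an amendment of protocol wording. The visits and MRI are already scheduled, so no new data are needed. The real price is the false-pause probability, which rises with accrual length and should be recalculated from the actual start date.
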